## Study Protocol

This experiment will test the app for proof of concept on older subjects with dizziness in a clinical environment (laboratory or clinic) under the supervision of a clinician. The aim is to test whether when using the app older patients perform rehabilitation in a similar manner as when directly instructed by a clinician. A secondary goal is to evaluate usability and enjoyment of the app. Data will be collected on 40 subjects (20 male and 20 female). Subject inclusion criteria are to be aged between 60 and 75, able to walk and get up from a chair independently, free of musculoskeletal disorders, and not taking any medication that may affect balance. Each participant will be asked to take part in two visits. One for the experimental trial and the other for a focus group follow up.

The subject age, body height and mass and vestibular condition will be recorded. They will also be asked to answer a Dizziness Handicap Inventory (DHI) as well as an Activities-specific Balance Confidence (ABC) scale questionnaire to assess how much they are affected by their vestibular condition.

Each subject will perform a rehabilitation session with the prototype app and one session without the app. The session will be setup on the app by the clinician for each participant specifically. The session without the app will include the same exercises at a similar recommended speed and range of motion. These will be performed without any feedback as they would typically be performed by a patient doing their at-home exercises. The order in which the sessions occur will be randomized to avoid learning effects. Subjects are encouraged to take a break between the sessions and can take a break at any time if desired. Each session will start with the participant practicing the games and exercises using the slower speed practice games and proceed when they feel ready. A physical therapist will be present to assist if needed. This is to simulate first use of the app. It is envisioned that the first time a patient will use the app this will be under supervision and assistance of a physical therapist. Patients will perform a full rehabilitation session, lasting about 20 minutes after that.

The real-time feedback during the exercises will be tested. A clinician who is blinded to the feedback the patient receives (as in they cannot see the screen and will be listening to music on headphones in the case of auditory feedback) will identify each error the patient makes and will make notes whether this error continues or is corrected by the patient. This will be coded with numbers and recorded on video. Errors identified by the ML algorithm will be stored in the app as well with a time stamp for comparison. Raw sensor data will be stored and analyzed to test the efficacy of the feedback and see if exercise execution improves after feedback.

IMU data will be collected during both sessions (with and without the app) for comparison. Outcome measures, including range of head motion, movement velocity, and the number of repetitions performed, will be calculated. Data will be compared between the two sessions to investigate whether patients performed exercises similar with and without the app. Questionnaires will be answered to rate usability and enjoyment while using the app, as well as

Questionnaires will be answered to rate usability and enjoyment while using the app, as well as open ended questionnaires to identify areas of improvement.

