Cover page

Official Title of the study: Individualized Vestibular Rehabilitation for Elderly With Self-Management and Gaming Elements

NCT number (if available): STUDY00148324

Date of the document: 3/4/2022

Statistical Design and Power

Number of subjects expected to enroll: 40

Expected effect size and power:

The expected effect size in head range of motion outcome measures (Flexion angle, Extension angle, Left angle, Right angle) is 5°. This is based on the mean and standard deviations of the data that were collected on 6 older vestibular patients in Phase I.

Using an estimated standard deviation of 7.5° and a desired power of 80% and a p<0.05, this resulted in an estimated 36 subjects being required to reach this power.

The expected effect size in head velocity outcome measures (Flexion angular velocity, Extension angular velocity, Angular velocity left, Angular velocity right) is 20°/s. This is based on the mean and standard deviations of the data that were collected on 6 older vestibular patients in Phase I.

Using an estimated standard deviation of 30°/s and a desired power of 80% and a p<0.05, this resulted in an estimated 35 subjects being required to reach this power.

Since effect size of the balance related outcome measures are unknown (these were not calculated in phase I), as well as the differences that will occur due to feedback (hypothesis 6) being unknown, a total number of 40 subjects was decided upon.

Statistical methods:

All outcome measures will be tested for normal distribution using a Kolmogorov-Smirnov test and if required non-parametric tests will be used. Statistical significance will be defined as p<0.05.

Hypothesis 3 will be test for significant difference for outcome measures for the exercises between performing the exercises with and without the app. This will be tested using a paired t-test. The two different conditions for the paired t-test are the exercises performed with and without the app. The outcome measures that will be compared between the two conditions are: Flexion angle, Extension angle, Left angle, Right angle, Flexion angular velocity, Extension angular velocity, Angular velocity left, Angular velocity right, Balance excursion medio-lateral, and Balance excursion anterior-posterior.

If any variable shows a non-normal distribution a Wilcoxon signed rank test will be used instead of a t-test.

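### Recommended speed and range are not stated to be matched or recorded across the two sessions, so a systematic gap would be confounded with the app in Hypothesis 3; nor can a signed paired test alone show similar performance

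*Protocol*

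**What the plan says.** In the Protocol (Study Protocol), the app session is individual: "The session will be setup on the app by the clinician for each participant specifically". The comparison session is described more loosely: "The session without the app will include the same exercises at a similar recommended speed and range of motion". It is also meant to be natural: "These will be performed without any feedback as they would typically be performed by a patient doing their at-home exercises". On sequence, "The order in which the sessions occur will be randomized to avoid learning effects".

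The stated aim is one of similarity: "The aim is to test whether when using the app older patients perform rehabilitation in a similar manner as when directly instructed by a clinician". The IMU comparison is session against session: "Data will be compared between the two sessions to investigate whether patients performed exercises similar with and without the app".

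The SAP (Statistical methods, Hypothesis 3) uses a paired t-test, or a Wilcoxon signed rank test if a variable is not normal: "The two different conditions for the paired t-test are the exercises performed with and without the app". The outcomes are achieved values, listed as "Flexion angle, Extension angle, Left angle, Right angle, Flexion angular velocity, Extension angular velocity, Angular velocity left, Angular velocity right, Balance excursion medio-lateral" and anterior-posterior balance excursion. None is expressed relative to a recommended value, and no measure of individual agreement is planned. Hypotheses 5 and 6 concern error detection and change after feedback; they do not compare the two sessions.

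**The concern.** There are two separate issues.

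**Confounding by the recommendation.** The recommended speed and range belong to the condition. If the no-app recommendation is, on average, slower or smaller than the app setting and patients follow it, achieved velocity or angle will differ between sessions even if the app changes nothing about execution. Randomising the order balances learning and fatigue, but the recommendation moves with the session. If the values are not recorded, the gap may not be recoverable afterwards.

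**Signed comparison against an aim of similarity.** A paired t-test asks whether the mean signed difference is zero, and the signed rank test asks the same of the centre of the differences. Opposite individual differences cancel in both. Because the hoped-for conclusion is that patients perform alike, cancellation works in favour of that conclusion.

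**Working it through.** **Inputs.** SAP, Expected effect size and power: effect 5° with SD 7.5°; effect 20°/s with SD 30°/s; power 80%; p<0.05; stated requirements 36 and 35; planned enrolment 40. Assumed: two-sided testing (the SAP does not say) and the sizes of the recommendation gap (the documents give none).

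**Step 1: which SD?** The SAP does not say whether 7.5° and 30°/s are SDs of paired differences or within-session SDs. Its own figure helps:

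- Independent-means formula, n = 2(1.960 + 0.842)² × (SD/effect)² = 2 × 7.849 × (7.5/5)² = 35.3, which rounds up to 36. The ratio 30/20 gives the same 35.3, so the stated 35 agrees within rounding.
- Exact paired t-test with 7.5° as the SD of differences: 20.

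The stated figures therefore fit within-session SDs with zero correlation, for which the SD of differences is 7.5 × √2 = 10.6° (30 × √2 = 42.4°/s). Both readings are carried forward.

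**Step 2: a systematic gap with no app effect.** The paired t-test with n = 40 has 39 degrees of freedom and critical value 2.023. If patients follow a mean gap g, the noncentrality is (g / SD of differences) × √40.

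| Assumed gap | SD of differences | Noncentrality | P(p<0.05) |
|---|---|---|---|
| 2.5° or 10°/s | 7.5° / 30°/s | 0.333 × 6.325 = 2.108 | 54% |
| 2.5° or 10°/s | 10.6° / 42.4°/s | 0.236 × 6.325 = 1.491 | 31% |
| 1.25° or 5°/s | 7.5° / 30°/s | 0.167 × 6.325 = 1.054 | 18% |
| 1.25° or 5°/s | 10.6° / 42.4°/s | 0.118 × 6.325 = 0.745 | 11% |

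The larger gap is half the SAP's expected effect and the smaller a quarter. Without a gap the figure is 5%.

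**Step 3: opposite individual differences.** Illustration by simulation (20,000 runs, n = 40): 20 patients have a true between-session difference of +10° and 20 of -10°, plus random variation.

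| SD of random variation | P(p<0.05) | Mean absolute difference | Share differing by more than 5° |
|---|---|---|---|
| 7.5° | 0.1% | 10.6° | 77% |
| 10.6° | 0.7% | 12.0° | 76% |

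The test almost never signals a difference although most patients differ by more than the SAP's expected effect. The ±10° pattern is an assumption, chosen to show the mechanism.

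**The case against.** **The documents do not say that the recommendations differ.** This stands. A reader might infer that a Hypothesis 3 difference would be an artefact of the recommendation, but the text only fails to ensure or record equality. The loose wording may just reflect that spoken instruction cannot be delivered exactly as a game paces it. Only a systematic gap that patients follow shifts the mean; random gaps from patient to patient add variance and lower power.

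**The size depends on the SD reading and on invented gaps.** This also stands. Quoting 54% and 18% alone would be one-sided, because the SAP's 36 is reproduced under the reading that gives 31% and 11%.

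**Individual spread is not evidence of cancellation.** Correct. With a mean difference of zero, 50% of patients differ by more than 5° if the SD of differences is 7.5°, and 64% if it is 10.6°. A reader might take this to show that the app pushes patients in opposite directions. Any zero-mean spread of that size gives the same shares, ordinary session-to-session variation included. The figures show only what a null mean can conceal.

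**Deviation from target is a different question.** A reader might conclude that Hypothesis 3 should be replaced by absolute deviation from the recommended value. The stated aim compares session with session. With a common target T, (A − T) − (B − T) = A − B, so the raw signed difference loses nothing. Absolute deviation also has its own blind spot: a patient 10° over target in one session and 10° under in the other scores zero, although the sessions differ by 20°.

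**A natural at-home comparator need not be tightly controlled.** True of feedback and supervision during the exercises. It is no reason to leave the recommendation given beforehand unmatched and unrecorded.

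**Conclusion.** The point holds as a gap in control and recording, with a possible bias and not a demonstrated one. A systematic gap that patients follow would be indistinguishable from an app effect. At half the SAP's expected effect it would give a significant result in 31% to 54% of trials with no app effect, and at a quarter in 11% to 18%. These figures rest on n = 40, two-sided alpha 0.05, a normal paired difference, the assumed gaps, and the two readings of the SAP's SDs.

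Independently of any gap, a non-significant signed test does not establish that patients perform alike. That follows from the form of the test and needs no assumption about the recommendations. The documents do not support going further, to a finding that the sessions will be prescribed differently or that the app causes opposing over- and undershoot.

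**What to change.** 1. In the Protocol's session description, replace the word *similar* so that the no-app session uses the same recommended speed and range as those set in the app for that participant. The no-app session stays without feedback. This sets no particular speed or range; it asks only that both sessions refer to one recommendation.
2. Record the recommended values for both sessions, before data collection starts.
3. In the SAP, keep the raw Hypothesis 3 comparisons. For each angle and velocity, add within-person agreement between sessions: the mean difference with limits of agreement, or the mean absolute between-session difference.
4. Deviation from the recorded recommendation may be reported descriptively.

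The cost is a wording change, a record of the set values, and some further summaries from IMU data already collected in both sessions. The documents do not say that the app stores a numerical value for each direction, so the record may need a short form. The added summaries should be labelled descriptive and not tested as additional hypotheses, since the SAP has no multiplicity plan. No new sample size can be derived, because the documents give no SD for these measures.

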Cover page

Official Title of the study: Individualized Vestibular Rehabilitation for Elderly With Self-Management and Gaming Elements

NCT number (if available): STUDY00148324

Date of the document: 3/4/2022

Statistical Design and Power

Number of subjects expected to enroll: 40

Expected effect size and power:

The expected effect size in head range of motion outcome measures (Flexion angle, Extension angle, Left angle, Right angle) is 5°. This is based on the mean and standard deviations of the data that were collected on 6 older vestibular patients in Phase I.

Using an estimated standard deviation of 7.5° and a desired power of 80% and a p<0.05, this resulted in an estimated 36 subjects being required to reach this power.

The expected effect size in head velocity outcome measures (Flexion angular velocity, Extension angular velocity, Angular velocity left, Angular velocity right) is 20°/s. This is based on the mean and standard deviations of the data that were collected on 6 older vestibular patients in Phase I.

Using an estimated standard deviation of 30°/s and a desired power of 80% and a p<0.05, this resulted in an estimated 35 subjects being required to reach this power.

Since effect size of the balance related outcome measures are unknown (these were not calculated in phase I), as well as the differences that will occur due to feedback (hypothesis 6) being unknown, a total number of 40 subjects was decided upon.

Statistical methods:

All outcome measures will be tested for normal distribution using a Kolmogorov-Smirnov test and if required non-parametric tests will be used. Statistical significance will be defined as p<0.05.

Hypothesis 3 will be test for significant difference for outcome measures for the exercises between performing the exercises with and without the app. This will be tested using a paired t-test. The two different conditions for the paired t-test are the exercises performed with and without the app. The outcome measures that will be compared between the two conditions are: Flexion angle, Extension angle, Left angle, Right angle, Flexion angular velocity, Extension angular velocity, Angular velocity left, Angular velocity right, Balance excursion medio-lateral, and Balance excursion anterior-posterior.

If any variable shows a non-normal distribution a Wilcoxon signed rank test will be used instead of a t-test.

Hypothesis 4 will be tested using the following outcome measures: Ease of use rating, Enjoyment rating, Motivation rating, Use intention rating, and Usefulness rating. It will be tested whether the mean and median for each of the outcome measures is a positive response (value < 4).

Hypothesis 5 will be tested similar to hypothesis 1 by calculating the accuracy of identifying the errors using the identification by the clinician as gold standard. The goal is to get a minimum accuracy of 90% for each specific error. This does not involve any specific statistical tests.

Hypothesis 6 will be using a paired t-test with pre- and post-feedback as conditions. Dependent variables will be average head range of motion and velocity and standard deviation of velocity over a time window pre- and post-feedback. This will be calculated for each common error separately. It will be tested if head motion is altered for the error of moving the body versus the head, it will be tested whether head motion slows down or speeds up as instructed by the

feedback and if movement velocity standard deviation reduces when feedback is given on an inconsistent speed.

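### The normality check is aimed at the outcome measures rather than the within-patient differences, so the rule choosing between paired t-test and signed-rank test can misfire

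*SAP*

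**What the plan says.** The Protocol (Study Protocol) has every subject do one session with the app and one without, in random order. The SAP, under Statistical methods, compares ten outcomes between those sessions by paired t-test for Hypothesis 3: four head angles, four angular velocities and two balance excursions.

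The distributional rule comes in two sentences. The general one is "All outcome measures will be tested for normal distribution using a Kolmogorov-Smirnov test and if required non-parametric tests will be used". The one attached to Hypothesis 3 is "If any variable shows a non-normal distribution a Wilcoxon signed rank test will be used instead of a t-test". For the feedback comparison, "Hypothesis 6 will be using a paired t-test with pre- and post-feedback as conditions"; only the general sentence covers it.

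The overall threshold is given ("Statistical significance will be defined as p<0.05"). The SAP does not say that differences are what is checked. It does not say whether the Kolmogorov-Smirnov (KS) test is corrected for an estimated mean and SD (Lilliefors), and it gives no separate level for the normality check.

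**The concern.** A paired t-test uses the data only through the differences, d = app minus no-app (or post minus pre feedback). A patient's general level cancels out of d but dominates the spread of the session values. A check on session values can therefore pass while a few patients have extreme differences, and can fail because patients vary in a skewed way although their differences are normal.

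The first error costs power. That matters here because the aim is to show that patients perform similarly with and without the app, while the test looks for a difference. A true difference that is missed would tend to be read in the app's favour. The SAP also says that effect sizes for the balance outcomes and for the feedback effect are unknown, so nothing in the documents shows that those differences are well behaved.

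**Working it through.** **Inputs from the SAP.** n = 40; significance level 0.05 (two-sided assumed; one-sided would give 28 subjects, not 36); power 80%; effect 5° with SD 7.5°; effect 20°/s with SD 30°/s. The documents give no distributions, so every shape below is an assumption.

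**1. The plan's own figure.** The SAP reports "a desired power of 80% and a p<0.05, this resulted in an estimated 36 subjects being required to reach this power". With (1.960 + 0.842)² = 7.85:
- Two-group formula: 2 × 7.85 × (7.5/5)² = 35.3, so 36. This reproduces the SAP. The velocity ratio is also 1.5 and gives 36; the SAP says 35, a trivial discrepancy.
- Paired formula with 7.5° as the SD of the difference: 7.85 × 2.25 = 17.7, so 18 (20 with the t distribution).
- Paired formula with 7.5° as a session SD and uncorrelated sessions: SD of the difference = √2 × 7.5 = 10.6°, and 7.85 × (10.6/5)² = 35.3, so 36.

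The SAP does not say which SD it means, so both readings are carried forward.

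**2. Why session values hide the differences.** Write the two session values as S + d/2 and S − d/2, where S is the patient's level. The session variance is then var(S) + var(d)/4. Assume a between-patient SD of 15, and differences with SD 5 in 90% of patients and four times that (20) in 10%. Then var(d) = 0.9 × 25 + 0.1 × 400 = 62.5, and the differences supply 15.6 / (225 + 15.6) = 6.5% of the session variance.

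**3. Rejection rates of the normality tests themselves at n = 40.**

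| Shape | KS, uncorrected | KS, Lilliefors | Shapiro-Wilk |
|---|---|---|---|
| Normal | <0.1% | 5.1% | 4.7% |
| t(3) | 8% | 41% | 56% |
| Chi-square(4) | 5% | 60% | 89% |
| Exponential | 24% | 90% | 99.6% |
| Lognormal, sigma 1 | 65% | 98% | 99.9% |

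Uncorrected KS is weak against moderate departures, but not against strong skew.

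**4. Power when differences are heavy-tailed and patient levels are normal.** The rule is applied to session values with uncorrected KS unless noted. Ranges are across repeat runs.

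| Scenario | Rule on session values | Better-aimed alternative |
|---|---|---|
| Shift 3, 10% of patients with 4 × SD (base SD 5) | 67–69% | 85–87% (Shapiro-Wilk on differences); 87–88% (signed-rank) |
| Shift 3, t(3) × 5 | 65–69% | 80–82%; 82–84% |
| Shift 3, either shape, Lilliefors on session values | 69–71% | as above |
| Shift 5, either shape at the same scale | about 95% | 99% or more |
| Shift 5, total SD of difference 7.5 | 97% | about 100% |
| Shift 5, SD of difference 10.6 | 81% | 96% |
| Shift 5, SD of difference 10.6, t(3), between-patient SD twice that of the difference | 87% (88% Lilliefors) | 90% (95% Lilliefors), same KS on differences |

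**5. Needless switching: skewed patient levels, normal differences.** Uncorrected KS on session values moves to the signed-rank test in about 24–42% of datasets (52% with lognormal sigma 1 levels and a between-patient SD twice that of the difference). Lilliefors does so in about 90%. In that last setting, power is 81–82% against 83% when the differences decide, and type I error is 5.2–5.3% either way.

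**6. Rejection rate at zero mean difference.** With symmetric differences it was 4–6% under every rule. With skewed differences:

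| Differences | Rule on session values | Automatic switch on differences |
|---|---|---|
| Lognormal, sigma 0.5 | 6.8% | 14% |
| Exponential | about 7.5–8% | about 19–21% |
| Lognormal, sigma 1 | 11–13% | 34–42% |

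The first two rows switch by Shapiro-Wilk, the third by KS. The signed-rank test assesses symmetry about zero, not the mean.

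**The case against.** The SAP does not use the words session values and does not say that KS is uncorrected. Both are inferences, although the first is the natural literal reading. This stands, and the point is therefore put conditionally.

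A reader might infer that the KS check is inert. The documents do not support that. It holds only for an uncorrected test and moderate departures; uncorrected KS rejects in 65% of lognormal (sigma 1) samples. Nor does the point depend on it, since at a shift of 3 Lilliefors on session values recovers only one or two percentage points of power.

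A reader might also infer that the rule picks the wrong test as a matter of course. It does not. If session values and differences are all normal, the uncorrected rule agrees with a check on the differences in essentially every run, and the Lilliefors version disagrees in about 13% with no material effect on error rates.

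The strongest objection concerns size. The large power gap belongs to a shift of 3, which the SAP does not plan for. At 5°, with 7.5° as the SD of the difference, power stays far above 80% under either rule. This stands too, with one limit: 36 subjects is not what that SD gives in a paired calculation (18). On the uncorrelated-session reading, which does give 36, the literal rule leaves power at about 81% where 96% was available.

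Finally, simply moving the check to the differences and keeping the automatic switch would raise false positives for the mean when differences are skewed (step 6). That is correct and shapes the fix.

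**Conclusion.** The point holds in limited form. The SAP states a rule for choosing the test and aims it at a quantity other than the one the paired t-test assumes to be normal. The rule can miss heavy-tailed differences and can switch when there is no need.

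The first failure costs from a few points of power (95% against 99% at 5°) to about 15 (81% against 96% at 5° with uncorrelated sessions; about 69% against 82–87% at a shift of 3). The second costs almost nothing. Type I error is not at risk from the rule when differences are symmetric; with skewed differences no version of the switch holds 5% for the mean.

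These sizes rest on assumed distributions, an assumed between-patient spread and n = 40 without dropout. No document reports outliers or the shape of the differences, so the plan cannot be said to lose this power, only to be unprotected against it. The sample size does not change. The gap applies to all ten Hypothesis 3 outcomes and, through the general sentence, to Hypothesis 6.

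**What to change.** In the SAP, Statistical methods, replace the two sentences on normality with text to this effect:

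- Distributional assumptions are assessed on the within-patient differences (app minus no-app for Hypothesis 3; post minus pre feedback for Hypothesis 6), using a Q-Q plot and, if a formal test is kept, Shapiro-Wilk or Lilliefors-corrected KS.
- The paired t-test and the signed-rank test are both reported for every outcome, one prespecified as primary and the other as sensitivity.
- With asymmetric differences the signed-rank test does not test the mean, so non-normality caused by skew does not trigger an automatic switch.

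It would also help to state whether 7.5° and 30°/s are SDs of session values or of differences, since the size of this problem depends on it.

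The cost is a few sentences and a few lines of output, with no new data. The small downside is two p-values per outcome, which is why the primary one must be named in advance.

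### The SAP tests the app and no-app sessions only for a difference, so the Protocol's similarity question has no decision rule, and p>0.05 alone cannot answer it

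*SAP*

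**What the plan says.** **Protocol, Study Protocol section.** The similarity question appears twice, with different comparators.

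- The opening paragraph says "The aim is to test whether when using the app older patients perform rehabilitation in a similar manner". The sentence then names the comparator as performance under a clinician's direct instruction.
- The paragraph on IMU data says "Data will be compared between the two sessions to investigate whether patients performed exercises similar with and without the app". Here the comparator is the no-app session, which the section describes as unsupported by feedback, like home exercise. The measures named are head range of motion, movement velocity and the number of repetitions.

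**SAP, Statistical methods.** "Hypothesis 3 will be test for significant difference for outcome measures for the exercises between performing the exercises with and without the app". The method is a paired t-test, replaced by a Wilcoxon signed rank test for non-normal variables, and "Statistical significance will be defined as p<0.05". Ten outcomes are listed: four angles, four angular velocities and two balance excursions. Repetitions are not among them.

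**SAP, Expected effect size and power.** The sample size rests on expected effects of 5° (SD 7.5°) and 20°/s (SD 30°/s), giving 36 and 35 subjects, with 40 planned. On their source the SAP says "This is based on the mean and standard deviations of the data that were collected on 6 older vestibular patients in Phase I".

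Neither document states a similarity margin, a confidence-interval rule or how a non-significant result will be read. Hypotheses 4 and 5, by contrast, have success criteria: a rating below 4 and 90% accuracy.

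**The concern.** The Protocol asks whether performance is similar. A difference test can fail to find a difference, but that is not the same as showing that any difference is tolerably small. A non-significant result may reflect imprecision. Equally, a precise study can find a difference that is significant but too small to matter.

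The comparison of sessions is the Protocol's only route to the similarity question, and no other criterion is given. The investigator would therefore reach the end of the study with p-values and no stated way to turn them into an answer. A margin chosen once results are known could be fitted to either conclusion.

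**Working it through.** **1. The plan's own figure.** Two-sided 5% level (assumed, as sidedness is not stated), power 80%.

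- Range of motion: N = 2 × [7.5 × (1.96 + 0.8416) / 5]² = 35.3, which rounds up to the stated 36.
- Velocity: 30/20 = 7.5/5, so N is again 35.3, against the stated 35.

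This is the per-group formula for two independent groups. It equals a paired calculation with zero within-person correlation, where the SD of differences is 7.5 × √2 = 10.6°. If 7.5° were itself the SD of differences, N = 2.25 × 7.849 = 17.7, which does not match. Either way it is a calculation for detecting a difference, with no margin in it.

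**2. Assumed SD of paired differences.** The SAP does not say which SD 7.5° is. If it is a one-session SD with within-person correlation r, the SD of differences is 7.5 × √(2(1 − r)).

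| Reading of 7.5° | SD of differences |
|---|---|
| One-session SD, r = 0.75 | 5.3° |
| SD of differences, or one-session SD with r = 0.5 | 7.5° |
| One-session SD, r = 0 | 10.6° |

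The last is the least favourable, although it reproduces the stated 36. The Protocol supports a positive correlation: "The session without the app will include the same exercises at a similar recommended speed and range of motion".

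**3. How the two rules can disagree.** n = 40, df = 39, t(0.975) = 2.0227, t(0.95) = 1.6849. The result is significant if the observed mean difference exceeds 2.0227 × SD/√40 in size. The 90% CI lies within ±5° if the mean difference is smaller in size than 5 − 1.6849 × SD/√40. With the sample SD equal to the assumed SD:

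| SD | Significant above | Within ±5° below | Zone of disagreement |
|---|---|---|---|
| 5.3° | 1.70° | 3.59° | 1.70–3.59°: significant, yet within |
| 7.5° | 2.40° | 3.00° | 2.40–3.00°: significant, yet within |
| 10.6° | 3.39° | 2.17° | 2.17–3.39°: non-significant, yet not within |

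**4. How often.** Probabilities integrate over the distribution of the sample variance and were confirmed by simulation to about 0.001. The ±5° margin is illustrative only.

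| Event (one angle outcome, n = 40) | SD 5.3° | SD 7.5° | SD 10.6° |
|---|---|---|---|
| True 2°: non-significant, CI not within ±5° | about 0% | 0.7% | 25% |
| True 2°: significant, CI within ±5° | 61% | 18% | 0.2% |
| True 0: non-significant, CI not within ±5° | 0% | 0.1% | 15% |
| True 5°: non-significant | under 0.1% | 1.6% | 17% |

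At SD 7.5° and a true 0, the third row rises to 5% at ±4° and 35% at ±3°.

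**5. What 40 participants could show.** Power per outcome for two one-sided tests (TOST, 90% CI within the margin):

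| Margin, true difference | SD 5.3° | SD 7.5° | SD 10.6° |
|---|---|---|---|
| ±5°, true 0 | over 99.9% | 99% | 80% |
| ±5°, true 2° | 97% | 80% | 54% |
| ±4°, true 0 | over 99% | 90% | 52% |
| ±3°, true 0 | 94% | 60% | 12% |

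For velocity the same percentages apply with every angle value multiplied by 4, in °/s.

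**The case against.** **The wording of Hypothesis 3 is not in the documents.** The SAP speaks of expected effects and sizes the study to detect them, which fits a hypothesis that a difference exists. A reader might infer that the paired t-test is the wrong test for Hypothesis 3. The documents do not support that: if the hypothesis expects a difference, the test suits it. What stands is that the Protocol's similarity question then has no analysis at all.

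**The aim's comparator is different.** The opening paragraph compares app use with direct clinician instruction, not with the no-app session. A physical therapist is present and speed and range are recommended, so the two may overlap, but the documents do not equate them. This objection stands. The point rests on the later with/without-app comparison, and a margin on that difference would not clearly answer the aim in the Protocol's opening paragraph.

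**The harm is conditional and may be small.** A reader might infer that the sponsor will declare similarity from p>0.05. No passage says so. At ±5° and an SD of 7.5° or less, a non-significant result with a CI not within the margin occurs in under 1% of trials at the true differences tried (0, 1, 2 and 5°). The large figures need zero within-person correlation or a tighter margin, and neither document gives a margin. This stands as a limit on size. The opposite disagreement would produce undue caution, not a false claim of similarity, though it could count against an app that works as intended.

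**It is a proof-of-concept study.** True, but the SAP plans formal tests and a power calculation for this very comparison, and the minimum repair is light.

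**Conclusion.** The concern holds in a limited form. The Protocol's with/without-app similarity question is met in the SAP only by a test for a difference, with no margin, interval rule or interpretation of p>0.05. On that analysis a non-significant result does not by itself establish similarity, and a small significant one does not by itself refute it.

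Confidence is high that the rule is absent, and lower about what Hypothesis 3 was meant to claim. The direction and frequency of disagreement depend on two things the documents leave open: the margin, and the SD of the paired differences. With smaller SDs the likelier disagreement is a significant difference that is still within the margin. With the largest SD it is a non-significant result that does not show similarity.

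Nor do the documents support a claim that 40 participants are too few. That number could be ample or inadequate depending on the margin and SD. The defect is the missing rule, not necessarily the sample size. It should be fixed, but it does not invalidate the design.

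**What to change.** **Minimum, in the SAP and Protocol text:**

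- Reconcile the comparator in the Protocol's stated aim (direct clinician instruction) with the no-app session that is actually compared, and state Hypothesis 3 in words.
- For every measure in the similarity comparison, report the paired mean difference with its CI, or a Hodges-Lehmann or bootstrap interval if non-normal. Include the number of repetitions, which the Protocol names but the Hypothesis 3 list omits.
- State that p>0.05 will not be read as similarity.
- Report the two balance excursions as estimates with CIs, since the SAP has no effect size for them.

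**If a similarity claim is intended:**

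- Base it on the 90% CI of the paired difference (TOST) against one angle margin and one velocity margin. The sponsor should justify both as tolerable differences and fix them before outcome data are examined.
- Do not adopt 5° or 20°/s by default. They are expected effects from 6 patients, not tolerable differences.
- State whether similarity is claimed outcome by outcome, or only if all eight angle and velocity outcomes meet their margins.

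**Cost.** The minimum needs only wording, with the same sessions, data and 40 participants. The 95% CI half-width would be about 1.7°, 2.4° or 3.4° for angles (6.8, 9.6 or 13.6°/s for velocities) across the three assumed SDs. The similarity claim carries a real downside: with a tight margin it may not be shown with 40 participants, and requiring all outcomes to meet their margins would give power no higher than the per-outcome figures above. In that case the conclusion is limited to estimates with CIs.
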